5.3 Secondary Endpoints

The following parameters are the secondary endpoints:

- **Response rate**
The response rates (complete response (CR), partial response (PR)) and overall response rate (CR or PR) are evaluated 4 weeks after the end of treatment.
- **Best response**

Best response is determined in the time interval from the start of therapy to end of follow-up

- **Time to best response**

Time to best response is defined as the time from the start of therapy to best response the patient achieves (CR, PR)

- **Time to first response**

Time to first response is defined as the time from the start of therapy to first response (CR, PR).

- **Progression free survival (PFS)**

Progression free survival (PFS) is defined as the time from registration to the first occurrence of progression or relapse as assessed by the investigator, or death from any cause. PFS for patients without disease progression, relapse, or death will be censored at the time of the last tumor assessment.

- **Time to treatment failure (TTF)**

Time to treatment failure (TTF) is defined as the time of registration to discontinuation of therapy for any reason including death from any cause, progression, toxicity or add-on of new anti-cancer therapy. Patients alive without treatment failure are censored at the latest tumor assessment date.

- **Duration of Response (DR)**

Duration of Response will be calculated in patients with response (CR, PR) to therapy from diagnosis of response to the date of progression, relapse or death from any cause. Patients alive without progression and relapse will be censored at the latest tumor assessment date or the stopping date.

- **Cause specific survival (CSS)**

Cause specific survival is defined as the period from the study registration to death from lymphoma or lymphoma related cause; death unrelated to MZL is considered as a competing event.

- **Overall survival (OS)**

Overall survival is defined as the period from the induction registration to death from any cause. Patients who have not died until the time of the analysis will be censored at their last contact date.

- **Quality of life during trial**

Quality of life will be measured by the FACT Lym (see Appendix I) before start of treatment and during trial participation.

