9.5 Follow-Up Assessments

Neither in the case of CR/SD nor in the case of PD is it necessary to provide the study medication beyond the end of the study. In the case of PD, treatment is continued with a different treatment regimen.

a. Patients with response or stable disease

For patients who have at least SD at the EOT visit, disease assessments will continue every 3 months ± 14 days for 2 years (with CT/PET-CT/MRI if initially positive or indicated every 6 months) and then every 6 months ± 14 days for 3 years (with CT/PET-CT/MRI if initially positive or indicated every year) until the end of the study or until disease progression, whichever occurs first. This assessment is consistent with both NCCN and ESMO guidelines. Patients will then be followed twice per year until the end of the study for the following:

- New anti-lymphoma therapy
- Survival

Patients who start a new anti-lymphoma therapy or discontinue study drug in the absence of disease progression should be followed according to the above schedule.

b. Patients with disease progression

Patients with disease progression at any time will be followed every 6 months (after early completion visit) until the end of the study (approximately 7.5 years after inclusion of first patient) for the following:

- New anti-lymphoma therapy
- Survival

10. Study procedures

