For the analysis of the overall response rate (CR or PR), a new variable *ORR* (yes/no) will be calculated from the variable *ASS_RESULT* as follows: IF *ASS_RESULT* in (1 2) THEN *ORR* = 1; ELSE *ORR* = 0;

Absolute and relative frequencies will be calculated for the statistical analysis of the variables *ASS_RESULT* and *ORR*.

Details for b): Best response (CR, PR, SD, PD) is determined in the time interval from the start of therapy to end of follow-up. At first, the single categories for the analysis of the response rates (CR, PR, SD, PD, NE) will be defined and calculated as described in section 'Details for a)' (see above) for each point in time in which a tumor assessment was performed and a new variable *THERAPY_RESULT* will be created. The best response for a patient is the minimum (i.e. the best outcome) of the variable *THERAPY_RESULT*, measured across all points in time with tumor assessment (over the entire observation time). The result is stored in a new variable *BEST_RESPONSE*.

Details for c): Time to best response is defined as the time from the start of therapy to best response the patient achieves (CR, PR). For calculation, the difference between the date of the first day of treatment in cycle 1 (*C1/D1*; see CTP pages 106-110) (variable *EXSTDAT* for *ACTIVITYID* = '*C1D1_SV*' in table **EX1**) and the date of best response (i.e. first date at which CR is reached; in case of no CR is reached, the first date at which PR is reached) will be used. For the determination, the variable *THERAPY_RESULT* (see section 'Details for b)' above) will be used, together with the date of assessment which is calculated as variable *ASS_DATE* from the variables *RSDAT_NMZEG*, *RSDAT_EGM* and *RSDAT_SMZ* in table **RS**. Patients who reach CR or PR: The earliest date at which CR or PR is documented will be determined for each patient across all points in time with tumor assessment and will be used as end date for time to best response (not censored). Patients who do not achieve the response category CR or PR, will be censored at the latest tumor assessment date.

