Details for d): Time to first response is defined as the time from the start of therapy to first response (CR, PR). For calculation, the difference between the date of the first day of treatment in cycle 1 (*C1/D1*; see CTP pages 106-110) (variable *EXSTDAT* for *ACTIVITYID* = '*C1D1_SV*' in table **EX1**) and the date of first response (first date at which CR or PR is reached) will be used. For the determination, the variable *THERAPY_RESULT* (see section 'Details for b)' above) will be used, together with the date of assessment which is calculated as variable *ASS_DATE* from the variables *RSDAT_NMZEG*, *RSDAT_EGM* and *RSDAT_SMZ* in table **RS**. Patients who reach CR or PR: The earliest date at which CR or PR is documented will be determined for each patient across all points in time with tumor assessment and will be used as end date for time to first response (not censored). Patients who do not achieve the response category CR or PR, will be censored at the latest tumor assessment date.

Details for e): Progression free survival is defined as the time of registration to the first occurrence of progression or relapse as assessed by the investigator, or death from any cause. PFS for patients without disease progression, relapse, or death will be censored at the time of the last tumor assessment. Progression free survival will be calculated as difference between time of registration (date of patient signed written informed consent; variable *RFICDAT* in table **DM**) and the earliest date of the event (progression or relapse or death) or the date of last tumor assessment (in case of no event). For the earliest date in case of progression or relapse the dates in table **RS** will be used as follows: nodal MZL and extragastric MALT lymphoma: variable *RSDAT_NMZEG* for *RSORRES_NMZEG* = 4, extranodal gastric MALT lymphoma: variable *RSDAT_EGM* for *RSORRES_EGM* in (4 5), splenic MZL: variable *RSDAT_SMZ* for *RSORRES_SMZ* = 4. Additionally for the date of progression, the variable *RSDAT_ET* (table **DSET** IF *DSDECOD_ET* = 3) will be used for identifying patients with PD. For patients who died, the date of death will be determined using the variable *DTHDAT* in table **DSEOS**.

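### Best response and the times to response have no cut-off at new anti-lymphoma therapy, so a response to a later treatment could be credited to pembrolizumab/rituximab

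*SAP*

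**What the plan says.** **Window for best response.** Protocol 5.3: "Best response is determined in the time interval from the start of therapy to end of follow-up". SAP 7.5 b) implements this by coding a response category at every tumour assessment (THERAPY_RESULT) and taking the patient's minimum, "measured across all points in time with tumor assessment (over the entire observation time".

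**Times to response.** SAP 7.5 c) and d) start at cycle 1 day 1 and use the same THERAPY_RESULT. Under d): "The earliest date at which CR or PR is documented will be determined for each patient across all points in time with tumor assessment". Section c) has the parallel sentence, and that date "will be used as end date for time to best response (not censored". Both sections have one censoring rule: "Patients who do not achieve the response category CR or PR, will be censored at the latest tumor assessment date".

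**Follow-up.** Protocol 9.5 a) says that for patients with at least stable disease (SD) at the EOT visit "disease assessments will continue every 3 months" for two years, then every six months for three years, with imaging at set intervals. It adds: "Patients who start a new anti-lymphoma therapy or discontinue study drug in the absence of disease progression should be followed according to the above schedule". After progression, protocol 9.5 b) and SAP 7.2 follow only new therapy and survival.

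**New therapy elsewhere in the SAP.** SAP 7.5 f) makes the start of new anti-cancer therapy (PRSTDAT in table PR2) an event for time to treatment failure (TTF). Sections b), c) and d) do not use that date.

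**The concern.** In a single-arm trial, best response and the response curves will be read as activity of the combination. That reading needs each counted response to have occurred before any other lymphoma treatment began. The rule does not ensure this. A patient who ends study treatment with SD, starts another therapy without documented progression, and reaches complete remission (CR) on it would be a CR for best response and an event for both times to response.

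The SAP would then hold two conflicting descriptions of one patient: failure at the start of the new therapy for TTF, complete responder some months later for best response.

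The documents leave room for this. Protocol 10.4.1 allows treatment to stop without progression (toxicity, or patient or physician decision) with follow-up continuing as planned. Protocol 8.5 lifts the ban on other therapies 110 days after the last study drug. For gastric disease with persistent sites, a footnote to the follow-up flowchart in Appendix A repeats endoscopy every three months until it is negative, with no condition on treatment given meanwhile.

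**Working it through.** The plan states no figure to reproduce. The check applies its rules to one invented patient, then sizes the effect.

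**1. Timeline, in days after cycle 1 day 1**

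- Cycle 10 day 1 staging: 9 × 21 = 189. Assume SD.
- Last study drug, cycle 18 day 1: 17 × 21 = 357.
- EOT visit four weeks later (protocol 9.4): 357 + 28 = 385. Assume SD.
- Earliest day on which protocol 8.5 no longer prohibits other therapy without progression: 357 + 110 = 467. Assume new therapy starts then.
- Follow-up staging on day 600 (invented): CR.

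**2. The two rules on this patient**

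| Quantity | Rule as written | Cut-off at new therapy |
|---|---|---|
| Best response | CR | SD |
| Time to best response | 600 days, event | 385 days, censored |
| Time to first response | 600 days, event | 385 days, censored |

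The result is the same for any new-therapy start between days 385 and 600.

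**3. Which patients can change**

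- Best response changes only if the category after the switch is better than every category before it.
- Time to first response changes only for a patient with no CR or partial remission (PR) before the switch.
- For PR on study followed by CR after the switch, time to best response depends on which sentence of SAP 7.5 c) governs: one uses the first CR date, a later one the earliest CR or PR date. That inconsistency is a separate matter.

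**4. Direction**

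A minimum over more assessments cannot become less favourable, so late assessments can only raise the CR rate and the CR-or-PR rate. SD to CR or PR moves the combined rate; PR to CR moves only the CR rate.

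The time endpoints have no single direction. The patient above stays at risk from day 385 to day 600 and then has an event. This can slightly lower the one-minus-survival curve in between, and raises it only from the late event on.

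**5. Size**

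SAP 2.1 gives 22 included patients. If all are analysed, one patient is 1/22 = 4.5 points and three are 3/22 = 13.6 points. The denominator is the Core Analysis Population, which excludes withdrawals. If the expected 15% withdrew, 22 × 0.85 = 18.7, about 19, and one patient would be 1/19 = 5.3 points.

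Two-sided 95% Clopper-Pearson intervals, the method of SAP 8.2.3, for illustrative counts:

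| Complete responders | Rate | 95% interval |
|---|---|---|
| 12/22 | 54.5% | 32.2 to 75.6 |
| 13/22 (one late CR added) | 59.1% | 36.4 to 79.3 |
| 15/22 (three added) | 68.2% | 45.1 to 86.1 |
| 17/22 | 77.3% | 54.6 to 92.2 |
| 18/22 (one added to 17) | 81.8% | 59.7 to 94.8 |

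SAP 8.2.3 allows these limits to be compared with a fixed value without naming one. If it were the 56% of the primary test, one misattributed CR could carry the lower limit across it (54.6 to 59.7).

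**6. What the rule does not touch**

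The primary endpoint, response rate a) and the start of duration of response all use the EOT assessment (EOT_ASS).

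**The case against.** The strongest reply is that this is a possibility, not a finding about the data. A patient must start new therapy without progression, still be staged, and then improve beyond anything reached on study treatment. The protocol expects a change of regimen mainly at progression: section 9.5 describes it for progressive disease, and section 8.5 assumes radiotherapy only then. The documents give no count of patients starting new therapy. This stands, and it limits the claim to what could happen.

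In protocol 9.5 the sentence on new therapy directly follows a twice-yearly follow-up for new therapy and survival only, so the schedule it points to is not beyond doubt. The staging schedule is the more natural reading, because the sentence sits in the part on patients without progression and that part's main schedule is disease assessment. The ambiguity should be acknowledged.

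The endpoints are exploratory, and SAP 8.2.3 calls their results hypothesis generating. That lowers the importance but does not make the attribution right.

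A reader might infer three stronger things that the documents do not support:

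- **That the SAP departs from the protocol.** It does not; the window is the protocol's.
- **That responses after progression will routinely be counted.** No staging is scheduled after progression, so one could enter only through an unscheduled recorded assessment, which the rule would not exclude.
- **That the times to response are biased towards a better result.** The change is a late event in place of censoring, which lengthens the recorded time.

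**Conclusion.** The concern holds in limited form. As written, the derivation of best response, time to best response and time to first response can credit the study combination with a response that followed another anti-lymphoma therapy, and nothing elsewhere in either document prevents it. For best response the error can only be upwards, by about 4.5 points per affected patient if all 22 are analysed and somewhat more if withdrawals reduce the denominator. For the two time endpoints it replaces censoring with a late event.

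This assumes that patients who switch without progression stay on the disease-assessment schedule. The number affected is not given and may be zero, so the documents do not show that the reported rate will be inflated. The confirmatory result is not at risk. The change is worth making because the correction is specific and the date it needs is already in the SAP.

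**What to change.** In SAP 7.5 b), c) and d), use only tumour assessments up to the earlier of first progression or relapse and the start of new anti-lymphoma therapy (PRSTDAT in PR2, first record per patient, as in f)). If there is no CR or PR by then, censor both times to response at the last such assessment.

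Record this in SAP section 3 as a change from the protocol 5.3 definition. Report the protocol-defined version as a sensitivity analysis, with the number of patients whose result differs. If none differ, a sentence saying so is enough.

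The programming cost is one date condition, applied before the minimum and the earliest response date are taken. The other costs are a documented departure from a protocol definition of exploratory endpoints and a best-response rate that may be slightly lower.

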7.2 Variables measured during Follow-Up

Variables measured during Follow-Up cover the following: ECOG Performance Status, B symptoms, hematology, serum chemistry, urine analysis, HBV DNA PCR, new anti-lymphoma treatment, survival follow-up, CT/MRI scan and tumor assessment (if initially positive), leukocyte immunophenotyping (FACS), quantitative immunoglobulins (IgA, IgG, IgM), serum protein immunofixation (if positive before), bone marrow aspirate and biopsy, and QoL questionnaire (FACT-Lym). Details are mentioned in part 7.1, see above. Patients with disease progression will be followed for new anti-lymphoma treatment and survival twice per year until the end of the study. Patients, who have not progressed so far, will be observed according to the follow up schedule in the CTP.

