- progression and relapse: For the date in case of progression or relapse the data in the tables *RS*, *DSET*, and *DSEOS* will be used as described in section 'Details for e)', see above
- death from any cause: For patients who died, the date of death will be determined using the variable *DTHDAT* in table *DSEOS*

In case of an event is the event date for remission duration the earliest date among these dates. Patients alive without progression and relapse will be censored at the latest tumor assessment date or the stopping date.

Details for h): Cause specific survival is defined as the period from the study registration to death from lymphoma or lymphoma related cause; death unrelated to MZL is considered as a competing event. CSS will be calculated as difference between time of registration (date of patient signed written informed consent; variable *RFICDAT* in table *DM*) and the date of an event (variable *DTHDAT* for *SURVSTAT* = 0 and *PRCDTH_DDORRES* = 1 in table *DSEOS*). Patients who have not died or died from another reason than lymphoma or lymphoma related cause until the time of the analysis will be censored at their last contact date.

Details for i): Overall survival is defined as the period from the registration to death from any cause. Overall survival will be calculated as difference between time of registration (date of patient signed written informed consent; variable *RFICDAT* in table *DM*) and the date of death (variable *DTHDAT*

for *SURVSTAT* = 0 in table *DSEOS*). Patients who have not died until the time of the analysis will be censored at their last contact date.

Details for j): Quality of life was measured by the FACT Lym before start of treatment and during trial participation. For statistical analysis, the FACT-Lymphoma Trial Outcome Index (TOI), the FACT-G total score, the FACT-Lymphoma total score and the sum score for each of the five subscales (physical well-being (PWB), social/family well-being (SWB), emotional well-being (EWB), functional well-being (FWB), lymphoma subscale (LYMS)), will be calculated. Details about the calculations are provided in two separate documents doc01_Administration Guidelines_Manual_082505.pdf and doc19_ScoringFACT-Lym v4-REVISED.pdf.

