8.2.3 Efficacy Analysis of Secondary Endpoints

All secondary endpoints (Response rate, Best response, Time to best response, Time to first response, PFS, TTF, DR, CSS, OS and Quality of life during trial (therapy)) will be analysed exploratory by respective descriptive analysis, statistical tests and two-sided 95%-confidence intervals. Missing values will not be replaced.

Response rate and best response: The rates incl. the two-sided 95% confidence intervals (Clopper-Pearson) will be provided. The confidence limits can be used for a comparison with a fixed value.

Time to best response, time to first response, PFS, TTF, RD, CSS, OS: Kaplan-Meier plots will be provided. Because time to best response and time to first response describe a favourable event, the ordinate of the Kaplan-Meier plot will be "1 minus survival probability" instead "survival probability".

Quality of life during trial: The FACT-Lymphoma Trial Outcome Index (TOI), the FACT-G total score, the FACT-Lymphoma total score and the sum score for each of the five subscales (PWB, SWB, EWB, FWB, LYMS), will be analysed as continuous variable.

With exception of the efficacy analysis of the primary endpoint, each statistical test will be performed two-sided at a significance level of 5%. All results from these analyses will be regarded as hypothesis generating only and not as proof of efficacy.

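### Time to response is plotted as 1 minus Kaplan-Meier with progressed or dead non-responders censored, which can overstate response; cause-specific survival censors deaths that the SAP itself defines as competing events

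*SAP*

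**What the plan says.** **Time to response.** SAP 7.5, details for c) and d), gives the same rule for time to best and time to first response: "Patients who do not achieve the response category CR or PR, will be censored at the latest tumor assessment date". Progression and death without response get no separate treatment. SAP 8.2.3 then plans the estimator: "Time to best response, time to first response, PFS, TTF, RD, CSS, OS: Kaplan-Meier plots will be provided". It adds: "Because time to best response and time to first response describe a favourable event, the ordinate of the Kaplan-Meier plot will be" one minus the survival probability.

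**After progression.** SAP 7.2 says: "Patients with disease progression will be followed for new anti-lymphoma treatment and survival twice per year until the end of the study". Protocol 9.5 b is to the same effect. The last tumor assessment of a progressed non-responder is therefore normally the one that showed progression.

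**Cause-specific survival.** Protocol 5.3 states that "death unrelated to MZL is considered as a competing event". SAP 7.5, details for h), repeats that definition. The same paragraph then says: "Patients who have not died or died from another reason than lymphoma or lymphoma related cause until the time of the analysis will be censored", the date being that of last contact. The plot planned in SAP 8.2.3 is again Kaplan-Meier.

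No cumulative incidence estimator is named for any of these endpoints. The SAP's only mention of cumulative incidence, in 2.1, concerns secondary malignancies.

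**The concern.** Censoring assumes that the censored patient could still have the event later, at the same rate as those who remain at risk. That is not so for a patient who died without response. Nor is it so, for response to study treatment, for a patient who progressed: Protocol 6 counts progression on treatment as treatment failure, and Protocol 10.4.1 ends per-protocol treatment. With these patients censored, 1 minus Kaplan-Meier describes response in a setting where progression and death do not occur, not the share of treated patients who respond by a given time.

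The trial stopped at 22 patients (SAP 3), so the descriptive curves will be read as results. A response curve that ends above the best-response proportion in the same report would flatter the treatment. For CSS, two sentences of one paragraph call for different analyses.

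**Working it through.** The documents give no figure for time to response or CSS, so there is nothing to reproduce. They also give no counts of progression or death before response. All event counts and hazards below are assumptions.

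**Inputs from the documents.** N = 22 (SAP 3). Response evaluation during treatment is at C10D1 and at end of treatment (Protocol 9.1.2). With 21-day cycles, C10D1 falls at 9 × 3 = 27 weeks. C18D1 falls at 17 × 3 = 51 weeks, and the end-of-treatment visit 4 weeks later is at 55 weeks.

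**General relation.** At each response time, with d responders among n at risk, 1 minus Kaplan-Meier rises by S(t−) × d/n, where S falls only at responses. The Aalen-Johansen estimate rises by A(t−) × d/n, where A falls at responses and at competing events. Since A is never above S, 1 minus Kaplan-Meier is never below the cumulative incidence. It is strictly above once a competing event precedes a later response.

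**Main illustration.** Assume 3 patients progress or die before week 27, 10 respond at week 27, 2 progress at that staging, and 3 of the remaining 7 respond at week 55.

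- SAP rule: 19 at risk at week 27 and 7 at week 55, so 1 − (9/19)(4/7) = 1 − 36/133 = 72.9%.
- Aalen-Johansen: 10/22 + (7/22)(3/7) = 13/22 = 59.1%, which is also the proportion with best response CR or PR.
- Excess: 13.8 points.

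**Sensitivity to who the three early patients are.** If they were simply lost and censored, or withdrew and so left the Core Analysis Population (SAP 4), Aalen-Johansen gives 10/19 + (7/19)(3/7) = 13/19 = 68.4%. The excess is then 72.9 − 68.4 = 4.5 points.

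**Other assumed patterns, N = 22** (competing event = progression or death without response):

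| Competing before wk 27 | Respond wk 27 | Competing between | Respond wk 55 | 1 minus Kaplan-Meier | Cumulative incidence |
|---|---|---|---|---|---|
| 0 | 12 | 0 | 4 | 1 − (10/22)(6/10) = 72.7% | 16/22 = 72.7% |
| 1 | 12 | 0 | 4 | 1 − (9/21)(5/9) = 76.2% | 16/22 = 72.7% |
| 2 | 12 | 1 | 3 | 1 − (8/20)(4/7) = 77.1% | 15/22 = 68.2% |
| 3 | 12 | 2 | 3 | 1 − (7/19)(2/5) = 85.3% | 15/22 = 68.2% |
| 4 | 10 | 2 | 3 | 1 − (8/18)(3/6) = 77.8% | 13/22 = 59.1% |
| 0 | 12 | 6 | 4 | 1 − (10/22)(0/4) = 100% | 16/22 = 72.7% |
| 0 | 12 | 6 | 0 | 1 − 10/22 = 54.5% | 12/22 = 54.5% |

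The first and last rows show no excess. In the last, six patients progress, but nobody responds afterwards.

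**CSS.** With constant hazards a (lymphoma death) and b (unrelated death), the complement of Kaplan-Meier at time t is 1 − exp(−at). The cumulative incidence is a/(a+b) × [1 − exp(−(a+b)t)]. At 5 years:

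- a = 1%, b = 4% per year: 1 − exp(−0.05) = 4.9%, against 0.2 × [1 − exp(−0.25)] = 4.4%.
- a = b = 5% per year: 22.1% against 19.7%.

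In counts, with 22 patients and 2 unrelated deaths before 2 lymphoma deaths: 1 − 18/20 = 10.0% against 2/22 = 9.1%.

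**The case against.** The endpoints are secondary. SAP 8.2.3 treats their results as hypothesis generating, and no decision rests on these curves. The complete response test, the response rates and best response with Clopper-Pearson intervals do not depend on the censoring rule. Kaplan-Meier with censoring can also be read as net survival under independence, and Protocol 12.4 asks only for descriptive analysis and confidence intervals without naming an estimator for CSS. This limits the weight of the point but does not remove it: the net reading does not fit the competing-event definition that the SAP itself gives for CSS.

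Several stronger readings are tempting, and the documents do not support them:

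- A reader might infer that the response curve must end above the reported response rate. It does so only if a competing event precedes a later response, and no counts are given. The end-of-treatment rate is also the wrong comparator. Time to response uses all assessments, so even a correct curve can end above that rate. The comparator is the best-response proportion.
- A reader might infer that all censoring of non-responders is wrong. For those alive, progression-free and still assessed, it is proper.
- A reader might infer that the SAP has replaced the protocol's CSS definition. It repeats that definition and then contradicts it. The CSS curve is on the survival scale, so only its complement overstates lymphoma death.
- A reader might infer that new anti-lymphoma therapy has to be a competing event. Protocol 9.5 continues disease assessments after new therapy without progression, and SAP 7.5 c) and d) search all assessments for a response. Counting or not counting such responses is a choice of estimand.

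**Conclusion.** The point holds as a conditional one and should be acted on. As written, the rules can only push the response curves upward, never downward. The excess over cumulative incidence runs from zero to 18.7 points in the moderate assumed patterns and reaches 27.3 points in the extreme one. The 72.9% against 59.1% is not a forecast for this trial; it requires all three early patients to have progressed or died. Equality of cumulative incidence with the best-response proportion further assumes that no one is censored before a later response.

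For CSS the finding is mainly a contradiction within SAP 7.5 h), and between its censoring sentence and Protocol 5.3. Its numerical effect is about 0.5 to 2.5 points under the assumed hazards shown.

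**What to change.** In SAP 7.5 c) and d) and 8.2.3, replace 1 minus Kaplan-Meier with the Aalen-Johansen cumulative incidence for time to first and best response, with progression or death without prior response as competing events. Keep ordinary censoring at the last tumor assessment for non-responders who are alive and progression-free. State whether new anti-lymphoma therapy is also a competing event. If it is, say that responses documented after it then count toward best response but not toward these curves.

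In SAP 7.5 h), delete the part of the censoring sentence that covers unrelated deaths. Report the cumulative incidence of lymphoma death with unrelated death as the competing event, and change the CSS plot in 8.2.3 accordingly.

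The cost is SAP wording and a standard option in SAS or R, both already named in SAP 10. No new data are needed: SAP 7.5 e) and f) identify the dates of progression, death and new therapy, and SAP 7.4 the cause of death.
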